complete the BAARS-Self survey. To evaluate other services and treatments the participants may be receiving, they will complete the Service Utilization for College student's questionnaire. To measure treatment moderators and outcomes, they will complete the RCADS, Columbia Suicide Severity Index (required by NIMH), BDEFS, BAI-2, ADHD Impact Model-Adult (AIM-A), and surveys on Academic Record (GPA & Percentage of Assignments Completed), and a Reading Comprehension Standardized Assessment. Questions on feasibility and usability of the VR system will be asked. Outcome assessments will be performed by Rutgers study staff using Rutgers-hosted REDCap. Additionally, only for Phase 1 as part of the pilot process, participants will be asked to conduct a brief 15-min follow-up phone interview with a member of the research team to further elaborate on their questionnaire responses regarding their experiences with the virtual reality headset, the virtual study environment, and any issues they encountered while using the technology. This will provide valuable qualitative information for the LSU VR developer team to then improve the system for future phases of the study.

PHASE 2: Develop and refine contingency management algorithms.

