In-Session Assessment: As with Phases 1 and 2, participants will first complete 10 minutes of standardized reading comprehension passages and questions before being automatically prompted on their VR screen to complete 40 minutes of studying in either pass-through, VR immersive mode, or VR immersive mode with contingency management. After the allotted 40 minutes, participants will then be asked to complete 10 minutes of brief rating scales asking about feasibility/usability of using VR to complete work, attention/concentration, and homework effort. Specifically, participants will complete the Adult Concentration Inventory, the Homework Motivation Index, and the Homework Effort Index each session. Finally, they will answer a question about whether or not they took ADHD medication that day – the Current Day Medication Adherence. Participants will complete the 10-item Systems Usability Scale after sessions 4 and 12 only.

Outcome Assessment: Following the 12th session, participants will complete an outcome assessment. For the outcome assessment, they will complete some of the same outcome battery described in Phase 1 and 2 (BAARS-Self, BDEFS, BFIS, Academic Records, GPA & Percentage of Assignments Completed). Questions on feasibility and usability of the VR system will be asked in the outcome assessment. Outcome assessments will be performed by Rutgers study staff using Rutgers-hosted REDCap.

Follow-Up Assessment: Three months after the completion of the final session, participants will complete a follow-up assessment visit. The assessment battery will be the same as the outcome battery described in the initial outcome assessment. Follow-up assessments will be performed by Rutgers study staff using Rutgers-hosted REDCap.

PHASE 4: Conduct a larger parallel group randomized trial.

Phase 4 will follow the same procedures as Phase 3 (see above) except instead of n=45, we will randomize n=252 (note, number who consent is higher, to account for those found not eligible after consenting). This will be done across several cohorts. Please see the study timeline figure in section 1.10 for a visual of how many subjects will be in each cohort.

B. Data Points

PHASE 1: Refine objective data capture techniques.

Initial evaluation:

- Contact, demographic, and background information
- Service Utilization for College Students
- Current Day Medication Adherence survey
- BAARS-Self
- Pre-screening questions
- Adult Concentration Index (ACI)
- RCADS

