- Service Utilization for College Students
- Current Day Medication Adherence survey
- BAARS-Self
- Pre-screening questions
- Adult Concentration Index (ACI)
- GAD-7
- PHQ-9
- Columbia Suicide Severity Index
- WHODAS (Required by NIMH/NDA)
- DSM-5 Level 1 Cross-Cutting Symptom Measure (Required by NIMH/NDA)
- BDEFS – Short Form
- BFIS
- Baseline Homework Motivation Index
- Baseline Homework Effort Index
- Academic Record (GPA & Percentage of Assignments Completed)
- Reading Comprehension Standardized Assessment
- SCID-V RV

Each of 10 sessions:

- Key strokes and mouse clicks
- Reading Comprehension Standardized Assessment
- Periodic screenshots of participant screens
- 10-item Systems Usability Scale (Sessions 4 and 10 only)
- Adult Concentration Inventory
- Homework Motivation Index
- Homework Effort Index
- Current Day Medication Adherence

Outcome Assessments:

- Current Day Medication Adherence survey
- BAARS-Self
- BDEFS – Short Form
- BFIS
- Academic Record (GPA & Percentage of Assignments Completed)
- Feasibility and usability of the VR systems

3-Month Follow-Up

- Current Day Medication Adherence survey
- BAARS-Self
- BDEFS – Short Form
- BFIS
- Academic Record (GPA & Percentage of Assignments Completed)
- Feasibility and usability of the VR systems

C. Study Duration

PHASE 1:

Each participant will be involved for approximately 4 weeks (1 week of initial evaluation, 2 weeks of intervention, 1 week of outcome assessment).

The initial evaluation will take approximately 1.5 hours.

Each VR intervention session will take approximately 1 hour (10 minutes of reading comprehension questions, 40 minutes of intervention, 10 minutes to complete surveys). Across the intervention, they will complete 10 1-hour sessions.

The outcome assessment will take approximately 30 minutes to complete, and the follow-up phone interview with the research team should take 15 minutes.

PHASE 2:

Each participant will be involved for approximately 5 weeks (1 week of initial evaluation, 2 weeks of intervention, 1 week of outcome assessment, 1 week of focus group).

The initial evaluation will take approximately 1.5 hours.

Each VR intervention session will take approximately 1 hour (10 minutes of reading comprehension questions, 40 minutes of intervention, 10 minutes to complete surveys). Across the intervention, they will complete 10 1-hour sessions.

The outcome assessment will take approximately 30 minutes to complete.

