2.3 Other Resources

In the event that a subject finds the assessments and/or intervention mildly anxiety provoking, research staff members will express empathy and appropriate encouragement and reassurance. Risk of emotional distress will be minimized through effective rapport building and interactions with the subjects. A small percentage of subjects might initially feel disoriented or dizzy in the VR environment. Most subjects adjust quickly after taking a break or working in small chunks of time. Should discomfort become sufficient to pose distress for the subject, the research staff member will discuss these reactions to determine whether the subject wishes to continue completing the research procedures.

*Some of the questionnaires and interviews have items that ask about suicidality, and it is possible that subjects will endorse items pertaining to threat to self. These questionnaires are reviewed at their baseline assessment visit. If any items that endorsed suicidality or threat to self were checked by subjects, then the study staff will consult with the PI ([name], who is a licensed clinical psychologist) to complete a risk assessment to determine appropriate actions based on level of risk (e.g., presence of a plan, desire to act on the plan, and access to means to carry out the plan). (see 4.7E for protocol for steps following risk assessment).

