2. If it appears that participants are at moderately high, but not imminent risk for suicide, we will refer them to the appropriate places (e.g., going to the counseling center, filing a concern report with the university). The psychologist consults with the psychiatrists at Student Health and counselors at University Counseling Services via telephone to determine what action should be taken and to connect them to services that day.
3. If participants are at imminent risk for suicide, we will do the following, depending on their location:
 - a. Call the Rutgers or LSU counseling center, the counseling center's emergency number (if outside of business hours), or Rutgers or LSU PD. This is a highly unlikely scenario, but in the case that we do need to take these actions, we will obtain on the consent form participants' permission to release information to these parties.
 - b. If this is enacted, study staff will remain on videoconference or in the room with the participant to explain until they have direct crisis support. The participant will be made aware of who is being called and what is expected to happen next (e.g., if someone is being sent to the home).

These procedures are in line with what is used in clinical practice and psychological research. It is extremely rare and the steps outlined are unlikely to be needed, but the procedure is in place to keep all participants safe.

Additionally, on-going monitoring will ensure there is not significant deterioration from baseline in any subject's psychopathology (e.g., depressive symptoms). An increase of 25% or greater on measures of internalizing symptoms triggers a conference and review of records. In addition, participants who are in the top 10% of the sample at baseline are automatically reviewed at each timepoint. Further, any participant who endorses any of the items related to suicidal thinking is automatically reviewed at each timepoint to ensure there have been no increases (e.g., from sometimes to often).

E. Minimizing Risks of Harm

See above for a detailed description of risks of harm and study team response.

- **Certificate of Confidentiality**
N/A
- **Provisions to Protect the Privacy Interests of Subjects**

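### Phases 3 and 4 schedule no internalizing or suicidality scale after baseline, so two safety checks in Section 4.7 D have no data to work on

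*Combined protocol and SAP*

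**What the plan says.** Section 4.7 D commits the study to continuing surveillance for deterioration from baseline in any subject, without limiting this to particular phases. It sets three rules:

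- A change rule: "An increase of 25% or greater on measures of internalizing symptoms triggers a conference and review of records".
- A baseline-rank rule: participants in the top 10% of the sample at baseline are reviewed at every timepoint.
- A suicidality rule: "any participant who endorses any of the items related to suicidal thinking is automatically reviewed at each timepoint to ensure there have been no increases".

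Section 1.3 A describes the Phase 3 outcome assessment as "some of the same outcome battery described in Phase 1 and 2 (BAARS-Self, BDEFS, BFIS, Academic Records, GPA & Percentage of Assignments Completed"), together with feasibility and usability questions. Of the 3-month follow-up it says: "The assessment battery will be the same as the outcome battery described in the initial outcome assessment". For the main trial it says: "Phase 4 will follow the same procedures as Phase 3 (see above) except instead of n=45, we will randomize n=252".

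Section 1.3 B gives one joint list of data points for Phases 3 and 4. The GAD-7, PHQ-9, Columbia index and DSM-5 Level 1 measure stand under the initial evaluation. They do not reappear under the sessions, under "Outcome Assessments" or under the 3-month follow-up.

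**The concern.** The 25% rule and the suicidality rule both compare a later score with a baseline score. If the relevant items are never asked again, no comparison is possible and the rules cannot operate. The top-10% rule can identify people at baseline, but the later reviews would have no new score to look at.

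What is at stake is a safety commitment to the randomised participants. Section 6.3 marks both the data and safety monitoring plan and the monitoring board as not applicable. That leaves 4.7 D as the only score-based monitoring for deterioration that the protocol describes.

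**Working it through.** The plan states no figure to reproduce. The check sets the instruments that the 4.7 D rules need against each scheduled timepoint in Phases 3 and 4, using both the narrative (1.3 A) and the data-point list (1.3 B).

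| Timepoint, Phases 3 and 4 | Scales listed | Internalizing or suicidality scale? |
|---|---|---|
| Initial evaluation | GAD-7, PHQ-9, Columbia, DSM-5 Level 1, and others | Yes |
| Sessions | Concentration, homework motivation, homework effort, medication adherence, reading comprehension; usability at two sessions | None |
| Outcome | Medication adherence, BAARS-Self, BDEFS Short Form, BFIS, academic record, feasibility/usability | None |
| 3-month follow-up | Same as outcome | None |

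The DSM-5 Level 1 measure is in the joint Phase 3/4 list, although the 1.3 A narrative places it in Phase 4 only. This does not alter the result.

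The narrative and the list agree. The Phase 3 outcome battery is given in brackets as a closed list, follow-up repeats it, and Phase 4 inherits it. A broken table is therefore not a plausible explanation. The documents do not present any of the later scales as a measure of internalizing symptoms or suicidality.

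The earlier phases differ. The Phase 1 outcome battery in 1.3 A repeats the RCADS, the BAI-2 and the "Columbia Suicide Severity Index (required by NIMH"). Phase 2 repeats at least the BAI-2 and Columbia in its narrative, and its data-point list adds the RCADS. The rules have data there.

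Size:

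- Participants to be randomised in Phases 3 and 4: 45 + 252 = 297.
- Planned post-intervention assessments with full retention: 297 × 2 = 594, of which 0 include a relevant scale.
- Flagged by the top-10% rule: 0.10 × 45 + 0.10 × 252 = 4.5 + 25.2 = 29.7, about 30. This assumes one ranking measure, applied within each phase. Section 4.7 D does not name the measure. If the GAD-7 and PHQ-9 were each ranked, the total could lie anywhere from about 30 (same people) to 2 × 29.7 = 59.4, about 59 (no overlap).

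**The case against.** The strongest reply has four parts.

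- **Live contact.** Section 1.9 A says the outcome visit takes place by videoconference with study staff, and 1.3 A calls the 3-month contact a visit, though it also says REDCap is used. Suicidal thoughts could be reported there and would trigger the risk assessment. This is fair, and the documents are mixed on the mode of contact. But a conversation helps only if the participant discloses, and it gives no score for a 25% comparison.
- **Repetition may be intended.** In describing the initial evaluation, 1.3 A introduces the GAD-7 and PHQ-9 among measures of moderators and outcomes. The Phase 3/4 list also has other slips. It omits the AIM, which 6.1 names as a mediation outcome. It refers to 10 sessions where the narrative has 12, and puts the second usability rating at session 10 rather than 12. An unintended omission is therefore quite possible. Even so, the narrative omits the scales too, and staff following either text would not administer them.
- **Weak supporting text.** Section 2.3 says of the suicidality questionnaires: "These questionnaires are reviewed at their baseline assessment visit". That section covers all phases, so it does not show that review in Phases 3 and 4 is confined to baseline. Likewise, the NIMH remark in Phase 1 does not say that the requirement extends to repeat administration or to later phases. The conclusion does not rest on either.
- **Low risk and other safeguards.** The protocol regards participation as minimal risk. Staff ask about well-being before each session, and reported suicidality leads to a risk assessment and contact with a licensed psychologist. These safeguards are real and limit the seriousness of the gap. They depend on the participant speaking up, and the pre-session enquiries stop after session 12, about 3 months before the follow-up.

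**Conclusion.** The concern holds. As scheduled, the 25% trigger and the check for increased suicidal thinking cannot operate for any of the 297 participants to be randomised in Phases 3 and 4, and the top-10% review would have no new score. This rests on reading the schedule in 1.3 A and B as complete, which the agreement between the two supports.

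This should be fixed, but it does not threaten the trial's results: no primary, mediation or moderation analysis uses these later scores. The number of cases that would be missed cannot be estimated, because the documents give no expected rate of deterioration.

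**What to change.** Add the GAD-7, PHQ-9 and Columbia items to the Phase 3/4 outcome and 3-month REDCap batteries, in both 1.3 A and 1.3 B. State in 4.7 D which role reviews flagged online answers, and within what time, under the existing risk-assessment procedure. That procedure is now worded for live contact, with the assessment done before the visit ends. Thresholds and actions remain the investigators' decision.

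The cost is a few minutes of self-report. The documents give no completion times. Assuming 3 to 8 minutes for the added items:

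- Outcome assessment (30 minutes): 3/30 = 10% to 8/30 = 27% longer.
- 3-month follow-up (20 minutes): 3/20 = 15% to 8/20 = 40% longer.

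Staff time is needed to review flags, and asking about suicidality online creates a duty to respond. The 25% rule sets no minimum change: from a baseline score of 4 it fires at 4 × 1.25 = 5, a rise of 1 point. Flags among low scorers may therefore be frequent, and the investigators may wish to add a minimum change.

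If the sponsor prefers not to repeat the scales, 4.7 D should be reworded so that it does not promise score-based monitoring in Phases 3 and 4. That costs only a protocol amendment, but leaves monitoring dependent on disclosure.

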5.0 Special Considerations

5.1 Health Insurance Portability and Accountability Act (HIPAA)

N/A

5.2 Family Educational Rights and Privacy Act (FERPA)

N/A

5.3 Code of Federal Regulations Title 45 Part 46 (Vulnerable Populations)

A. Special Populations

- Students: The study is recruiting students at Rutgers University and Louisiana State University. The study staff will take every measure to minimize risk of coercion or undue influence by reminding subjects that they can change their mind at any time in the future regarding their enrollment in the study without any penalty to their status as a Rutgers or LSU student, and that their grades, student status, or the care they receive from a Rutgers or LSU program (e.g., Disability Services), and that their decision will not be communicated to anyone outside of the research staff.

5.4 General Data Protection Regulation (GDPR)

N/A

5.5 NJ Access to Medical Research Act (Surrogate Consent)

N/A

6.0 Data Management Plan

6.1 Data Analysis

Preliminary data analyses will include patterns of missing data, dropout rates, distributional properties of measures, and correlations among assessment measures. Continuous variables showing significant skewness or kurtosis will be transformed.

Phase 1: In addition, to calculating effect sizes, the ACI concentration items will be scored and examined for trends across VR sessions in relation to objective typing and mouse click algorithm and to questionnaires asking about homework effort and efficiency. The convergent validity threshold will be $>.50$ for associations between VR objective on-task assessment and self-report of concentration. This threshold is being used rather than $>.70$ given the multi-method nature of the comparison (i.e., objective to self-report). In addition, we will refine the algorithm by comparing scores to other objective metrics such as time spent on nonwork related websites and social media during each session. [name] accomplished this in pilot work using a combination of Google Chrome Plugins and a service such as Cyren which codes and categorizes websites accessed. To address the feasibility/usability aspect of the aim, participants will complete the Systems Usability Scale (Brown, 1996) and spend 10 minutes after each session with research staff providing feedback on ways to improve feasibility/usability of using the VR environment to complete homework and study for tests. The team will also explore whether adding in eye gaze tracking improves the accuracy of the algorithms.

Phase 2: This project incorporates the contingency management procedures. Trends in motivation across sessions will be evaluated in relation to objective and rating scale metrics of attention and to FlowLight data. Focus groups will be audio-recorded and transcribed verbatim. The focus group data will be analyzed inductively for information relevant to feasibility and acceptability of the protocol. Two study personnel will separately code notes taken during the focus groups for emerging concepts and themes. Initial analysis will consist of identifying concepts found within the data through open coding. Inter-rater reliability checks will be used to compare the themes generated. Coding will continue until the point of saturation, that is, when no new concepts emerge. Data will be systematically analyzed according to the principles of thematic analysis, a method commonly used in qualitative research of this nature.

Phase 3. Because these analyses will focus on evaluating preliminary intervention effect sizes, outcome analyses will be conducted separately for each target mechanism. To compare groups, the variable (e.g., objective attention) will be entered analysis of variance (ANOVA), which will yield effect sizes for time and for interactions of time by intervention. The primary dependent variables will be objective assessment of attention and ratings of concentration, as well as ratings of homework effort and homework motivation. We will also compare trajectories of objective attention data across the three conditions.

Phase 4. The mixed model methodology planned and incorporated by the SAS GLIMMIX procedure can accommodate missing response data, thus allowing us to make use of all available data; note that covariate measurements are taken at baseline and should not be missing. Using Bayes' estimation, individuals with more data are given more weight in the calculation. This procedure is preferable in comparison to listwise or pairwise deletion in analyses where portions of the developmental curve are represented by differing individuals. In addition, we will check to see whether missing observations are missing at random, where we will test whether treatment group or any other covariate has an effect on the missing information. Any covariate associated with missing data will be included in the final model. Mediational models

analyzed using MPlus will address missing data using full information maximum likelihood estimates. This approach makes full use of available data and is one of several procedures considered the state of the art for addressing missing data.

Intent to Treat Analysis: An intent-to-treat approach will be used to analyze the data, wherein each participant will be kept in the group to which they were randomized for analysis, regardless of treatment compliance. A mixed-effects model will be used to account for the repeated-measure nature of the study design. Time will be treated as a dummy-coded categorical variable using baseline as the reference. A student-level random effect will be included and modeled using an auto-regressive covariance structure to account for within-subject dependence due to repeated measurements. The models will also include treatment condition as a student-level fixed effect, and condition x time interaction effects. This modeling will allow us to compare baseline to 8-week (post) changes, and the extent to which these changes differ across conditions.

Mediator Analyses: Mediational analyses will be conducted using structural equation modeling. There are advantages of a structural equation modeling approach to estimating and determining the significance of indirect effects within mediational models and outlined specific estimation procedures that are available in MPlus. All analyses will be conducted in MPlus which provides estimates that partition the total effect of an independent variable on a dependent variable into the direct and indirect effects using bootstrap estimation procedures. Preliminary analyses will be conducted separately for each mediator. Scores on the mediator will be modeled as a function of pretest scores on the mediator, intervention condition, and covariates. The intervention's effect can then be partitioned into the direct effect on changes (e.g., on school grades) at posttest and follow-ups and the indirect effects via the mediator. These initial analyses will be used to guide a more comprehensive model that will incorporate mediators that emerge as significant within the individual models. Primary mediation analyses will focus on whether change in the proposed mechanisms of action mediates improvement in AIM total scores and BDEFS.

Moderator Analyses: Moderators will be examined in separate models incorporating each potential moderator variable into the previously described mixed effects models. Specifically, we will grand-mean center baseline scores on each moderator and incorporate both the main effect and Moderator x Group interaction term into each equation in the Level 2 model. For continuous measures, a significant interaction will imply moderation, with the size of the estimated coefficient reflecting the moderated change in treatment effect. Significant interaction effects can be followed up by testing the significance of the intervention effect across various levels of the moderator (e.g., 25th, 50th, and 75th percentile). For discrete measures, a significant interaction will again imply moderation, where we can directly compare the treatment effects between different levels of the potential moderator to gauge that moderator's effect.

